### 10.2. Secondary study parameter(s)

#### **Standard deviation (SD) of glucose values**

In patients who wear a continuous or flash glucose sensor the SD of the glucose values will be determined in the previous week before uploading the glucose data during the quarantine period. The SD will be compared to the SD during the last non-quarantine week.

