### 3. STUDY DESIGN

This study is an observational, cross sectional study to assess the impact of self-quarantining on glyceimic control, diabetes self-management, distress and well-being. Patients with type 1 and type 2 diabetes mellitus currently in care at the diabetes outpatient clinic of the LUMC will be eligible to participate and will receive information about this study and an informed consent form. A few days later they will be contacted by phone to resolve any questions they may have and ask if the patient wants to participate in the study. If patients want to participate, they will sign the informed consent form and send it to the LUMC by mail. Once informed consent is provided, patients will be sent an envelope including a fingerprick device and a small tube. They will be asked to fill the tube with several drops of blood up to a mark on the tube and send the envelope back to the LUMC postage free. At the LUMC the HbA1c will be measured by the clinical chemistry lab. If the patients wears a continuous or FSL sensor, sensor data will be collected according to standard clinical practice. Furthermore, patients will receive a link by e-mail to a set of online questionnaires, containing the DSMQ-R, SDSCA, PSS, PAID and WHO-5, along with questions about level of education, medication use, employment, social situation and the impact of self-quarantine on daily routines. The HbA1c measurement and questionnaire will be performed at least 6 weeks after starting the quarantine period but still within a period of quarantine measures. Questionnaires will assess the extent and impact of the quarantine measures for each individual patient and assess the effect on glyceimic control, distress and well-being. Data on HbA1c measurements in the 12 months prior to the period of nationwide self-quarantine will be retrieved from the electronic health record of each patient, if available.

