### 8.3. Study procedures

Eligible patients from the diabetes outpatient clinic will be sent a letter with study information and informed consent forms. Within several days after receiving the letter, patients will be contacted by phone and will be invited to participate in the study as well as given the opportunity to ask questions. If patients are willing to participate they will be asked to sign the informed consent form and send it back to the LUMC by mail. Once informed consent is provided, patients will be sent a HbA1c fingerprick measurement envelope. They will be asked to fill the tube with several drops of blood up to a mark on the tube and send the envelope back to the LUMC postage free. At the LUMC the HbA1c will be measured by the clinical chemistry lab.

If patients are using a continuous or flash glucose monitoring device data of the most recent 3 months will be collected according to standard clinical practice.

Additionally, patients will receive a link in their e-mail to a set of online questionnaires, containing the DSMQ-R, SDSCA, PSS, PAID and WHO-5, along with questions about level of education, medication use, social situation, employment, impact of self-

quarantine on daily routines, and health status.

The HbA1c measurement and questionnaire will be performed once two months after the start of the nationwide quarantine phase as a result of the COVID-19 outbreak.

Data on HbA1c measurements in the 6 months prior to the period of nationwide self-quarantine will be retrieved from the electronic health record of each patient.

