## 10. STATISTICAL ANALYSIS

- Categorical data: gender, level of education, type of diabetes, medication use, type of blood glucose measurements (fingerprick or glucose sensor (FGM/CGM)) will be presented by percentage and standard deviation (SD).
- Continuous variables: age, BMI, weight, height, HbA1c will be presented using the mean and the standard deviation (SD). Derived parameters: BMI will be calculated from height (m) and weight (kg) using the formula  $(\text{weight (kg)} / (\text{height (m)})^2)$  and will be presented as continuous variable by mean and standard deviation (SD). Glucose variability will be calculated by the standard deviation of the glucose values from the continuous and flash glucose monitors obtained during the previous week in the quarantine period. This SD will be compared to the SD from the glucose values during the last non-quarantine week. Other glyceic measures include time spent in range 4.0-10.0 mmol/l, time spent in hypoglycaemia (<3.0, 3.0-3,5, and 3.5-3.9 mmol/l), time spent in hyperglycemia ( $\geq 10.0$  mmol/l)
- Missing data will be excluded from analyses.

- Data will be statistically analysed using STATA intercooled 16.0. HbA1c measurements and SD measurements prior to and after the quarantine period will be compared using a paired-sample t-test in case of normal distribution or Wilcoxon Signed Rank Test in case of abnormal distribution. Furthermore, differences in HbA1c and glucose variability between patients with type 1 and type 2 diabetes will be measured using independent T-tests. Differences in well-being, distress and self-management between patients with type 1 and type 2 diabetes will be analysed using independent T-tests. The association between glucose variability and parameters for distress, well-being and self-management will be analysed using multivariate regression analysis.

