### **11.2. Recruitment and consent**

Patients with type 1 and type 2 diabetes that are currently in care at the diabetes outpatient clinic will be sent a letter with study information and informed consent forms. Within several days after receiving the letter, patients will be contacted by phone by a member of the study team and invited to participate in the study as well as given the opportunity to ask questions. If patients are willing to participate they will be asked to sign the informed consent form and send it back to the LUMC by post. Once informed consent is provided, patients will be sent an envelope with a lancet, small tube and instructions to collect blood with a fingerprick. They will be asked to fill the tube that is in the envelope with several drops of blood until the mark on the tube is reached and send the envelope (special envelope for medical samples) back to the LUMC. At the LUMC the HbA1c will be measured by the clinical chemistry lab.

If patients are using a continuous or flash glucose monitor, data will be collected according to standard clinical practice and will be covering the last non-quarantine week and the quarantine period.

Additionally, patients will receive a link in their e-mail to a set of online questionnaires, containing the DSMQ-R, SDSCA, PSS, PAID and WHO-5, along with questions about level of education, medication use, social situation, employment, impact of self-quarantine on daily routines.

The HbA1c measurement and questionnaire will be performed once at the predicted end of the nationwide quarantine phase as a result of the COVID-19 outbreak.

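### Glucose variability is compared on one sensor week per side although section 8.3 collects about three months of data, so the paired change is less precise than it could be and rests on one reference week

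*Protocol*

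**What the plan says.** Two places in the protocol fix the analysis window, and they agree. Section 10 takes the SD of the sensor values "obtained during the previous week in the quarantine period". Section 10.2 repeats this, adding that the week is the one before upload: "the SD of the glucose values will be determined in the previous week before uploading the glucose data during the quarantine period". It continues: "The SD will be compared to the SD during the last non-quarantine week". Neither gives a reason for one week. The test is a paired t-test or a Wilcoxon signed rank test.

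Two places describe which sensor data are collected, and they differ:
- Section 8.3: "data of the most recent 3 months will be collected according to standard clinical practice".
- Section 11.2: the data "will be covering the last non-quarantine week and the quarantine period".

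The date of the sensor upload is not stated. The nearest guide is the timing of the HbA1c sample and questionnaire, which has three versions:
- Section 3: "at least 6 weeks after starting the quarantine period but still within a period of quarantine measures".
- Section 8.3: "will be performed once two months after the start of the nationwide quarantine phase".
- Section 11.2: "will be performed once at the predicted end of the nationwide quarantine phase".

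Glucose variability is the first-listed secondary objective (section 2) and endpoint (section 8.1.2). It is part of hypotheses H1 and H4 and also appears in the Summary's paragraph on main parameters. It has no sample size or power statement.

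**The concern.** A patient's glucose SD varies from one week to the next for reasons unrelated to quarantine. With one week on each side, that noise enters the within-patient difference twice at full size. Averaging several weeks would reduce it, and section 8.3 appears to supply those weeks.

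Precision matters here because the outcome exists only in sensor users, a subset of unstated size within a sample planned for HbA1c. Section 10 also excludes missing data, so a sensor gap in either chosen week can remove a patient who has usable data in neighbouring weeks.

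The whole contrast also depends on one reference week, immediately before the national measures. Section 1 describes a fast-growing outbreak and anxiety among people with diabetes, so that week may have been unusual. This is plausible, but the documents do not show it.

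**Working it through.** **The plan's own figure.** The only sample size is for HbA1c. With a difference of 4, SD 11, power 90% and alpha 0.05 (two-sided assumed), the formula for two independent means gives 2 × (11 × (1.960 + 1.282) / 4)² = 158.9, so 159 per group. Invitations: 159 / (0.35 × 0.80) = 567.9, so 568. Both figures reproduce, and neither concerns glucose variability.

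**Weeks available under section 8.3.** Three months is 3 × 365.25 / 12 / 7 = 13.0 weeks, and two months is 8.7 weeks. Reference weeks in the download are 13.0 minus the weeks from quarantine start to upload:

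| Upload after quarantine start | Pre-quarantine weeks in the download |
|---|---|
| 6 weeks | 7.0 |
| 8.7 weeks (two months) | 4.3 |
| 10 weeks | 3.0 |
| 12 weeks | 1.0 |
| 13 weeks | 0 |

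The two-month timing therefore leaves about 4 reference and 8 quarantine weeks. From 13 weeks on, the download misses the reference week altogether. Under section 11.2 there is one reference week plus the whole quarantine period, whatever the upload date.

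**Variance of the paired change.** Let s² be the week-to-week variance of a patient's weekly SD, and τ² the between-patient variance of true change in units of s². Let v(m) be the variance of a mean of m weekly values, in the same units, with first-order autoregressive correlation φ between weeks. The two windows are taken as uncorrelated apart from the patient's stable level, which cancels. Then

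Var(change) / s² = τ² + v(pre) + v(quarantine).

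The one-week plan gives τ² + 2. The protocol supplies none of these inputs. Assumed ranges: φ from 0 to 0.5 and τ² from 0 to 2. Under them v(1) = 1, v(4) = 0.25 to 0.516 and v(8) = 0.125 to 0.313.

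| Weeks (reference / quarantine) | Largest gain: φ = 0, τ² = 0 | Smallest gain: φ = 0.5, τ² = 2 | SE ratio |
|---|---|---|---|
| 4 / 4 | 0.50 / 2 = 0.25 | 3.03 / 4 = 0.76 | 0.50 to 0.87 |
| 1 / 8 | 1.125 / 2 = 0.56 | 3.31 / 4 = 0.83 | 0.75 to 0.91 |
| 1 / 4 | 1.25 / 2 = 0.625 | 3.52 / 4 = 0.88 | 0.79 to 0.94 |

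Each entry is the variance relative to the one-week plan, and so also the relative number of sensor users needed for equal precision.

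**Illustration in mmol/l** (assumed: SD of true change 0.4, independent weeks). The SD of the change is √(0.16 + 2s²/k) for k weeks per side.
- s = 0.3: √0.340 = 0.58 for k = 1 and √0.205 = 0.45 for k = 4, a variance ratio of 1.7.
- s = 0.7: √1.140 = 1.07 and √0.405 = 0.64, a ratio of 2.8.

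These ratios correspond to 0.60 and 0.36 of the one-week variance, inside the 4/4 range above. Correlation between weeks would reduce the gain.

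**The case against.** The strongest objection is section 11.2. If the download holds only one pre-quarantine week, the one-week reference matches the data collected, and a longer reference window means changing the collection as well as the analysis wording. A late upload has a similar effect under section 8.3. This stands. A reader might infer from section 8.3 that four reference weeks are simply in hand, but that holds only if section 8.3 prevails over section 11.2 and upload is at about two months. Even under section 11.2, several quarantine weeks are collected and not used.

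Second, a longer window changes what is estimated. The week before upload is a coherent description of the current state, and the DSMQ-R asks about recent days. One might conclude that any longer window is simply better, but if the effect evolves during quarantine, averaging mixes phases. Against this, the PSS asks about the past month. At a six-week upload, the last four weeks still leave out the first two weeks of quarantine. Keeping the one-week contrast as a sensitivity analysis meets what remains.

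Third, two further effects might be inferred but are not supported:
- *Attenuated regression coefficients.* Section 10 does not say whether variability is the dependent variable in its regression on distress, well-being and self-management. If it is, as HbA1c is in the parallel model of section 10.2, random error widens standard errors and lowers R² but does not shrink the coefficients.
- *Bias towards zero.* This requires that behaviour had already shifted in the quarantine direction during the reference week. The documents do not show that. A four-week baseline would dilute such a shift to a quarter of its weight, not remove it.

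**Conclusion.** The point holds as one of precision and robustness for a secondary endpoint. The protocol explicitly chooses one week per side, gives no reason, and under either description of data collection leaves most quarantine weeks unused.

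Under the assumed ranges, four weeks per side would cut the standard error of the paired change by about 13% to 50%. If only one reference week exists, using eight quarantine weeks would cut it by about 9% to 25%. Over the values tested, averaging more weeks never raised the variance. The direction of the gain is therefore much firmer than its size.

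A reader might take glucose variability to be the main secondary outcome. The protocol lists it first but gives it no such rank, and the powered HbA1c comparison is untouched. The change is a cheap improvement that depends on first reconciling sections 8.3 and 11.2.

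**What to change.** 1. In sections 8.3 and 11.2, give one description of the sensor download, anchored to the quarantine start date. It should run from at least four weeks before that date through to upload.
2. In sections 10 and 10.2, define glucose variability per patient as the mean of the weekly SDs over the last four complete quarantine weeks before upload, compared with the mean over the last four complete pre-quarantine weeks. Average weekly SDs and do not pool the readings, because a pooled SD also picks up drift in mean glucose between weeks.
3. State a minimum number of usable weeks per side, for example two.
4. Keep the one-week comparison as a sensitivity analysis.

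The cost is small. Three months of data already cover four reference weeks for uploads up to about 13.0 − 4 = 9 weeks after the start. Each later week needs one more week of download. Some patients with short recordings will contribute fewer weeks. The quarantine value will describe the last month, not the latest week. Patients face no extra procedures.

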#### **Stress: PSS**

*Perceived Stress Scale (PSS)*: The PSS is a 10 item scale designed to measure the degree to which situations' in one's life are appraised as stressful (17). Participants rate each item based on their recall of the past month and the degree to which they perceived

events as being stressful on a 5 point scale (never –almost never – sometimes – fairly often – very often). Four positively stated items are the reverse scored and then all scores are summed for an overall perceived stress score with higher score representing more perceived stress. A validated Dutch version is available.

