### **Diabetes Self-Management: SDSCA and DSMQ-R**

*The Summary of Diabetes Self-Care Activities (SDSCA)* .The SDSCA is a short questionnaire that covers basic aspects of diabetes self-care in regards to general diet, specific diet, exercise, blood-glucose testing, foot care, and smoking (20). The core questionnaire consists of 11 questions but it can be expanded and adapted to specific needs using the additional self-care items published with the original instrument. The core set of questions has been validated in Dutch.

*The Diabetes Self-Management Questionnaire-Revised (DSMQ-R)* questionnaire is a revision of the original Diabetes Self-Management Questionnaire and contains 20- items that asks the patient about their self-management based on the previous days (21). These items can be grouped into four subscales (glucose management, dietary control, physical activity, and physician contact) from which an overall sum score for 'diabetes self-management' can be calculated. All subscales as well as the overall sum score have shown to be highly correlated with levels of HbA1c. Additionally, the revised version has an additional 7-item subscale containing questions specific to insulin usage intended for patients using insulin.

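### The glucose-variability week is anchored to the sensor upload, not the questionnaire, so one secondary regression can pair PSS and DSMQ-R scores with a week they do not describe

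*Protocol*

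**What the plan says.** **The glucose week.** Section 10.2 (Standard deviation (SD) of glucose values) states that "the SD of the glucose values will be determined in the previous week before uploading the glucose data during the quarantine period". The general text of section 10 describes the same quantity as "obtained during the previous week in the quarantine period" and names no anchoring event.

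**When the sensor data arrive.** Section 3 says "sensor data will be collected according to standard clinical practice". Section 8.3 says "data of the most recent 3 months will be collected according to standard clinical practice". Section 11.2 adds that the data "will be covering the last non-quarantine week and the quarantine period". None of the three gives an upload date.

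**When the questionnaire is completed.** It has its own timing, stated in three ways: at least 6 weeks into quarantine (section 3), two months after its start (section 8.3), and at its predicted end (section 11.2). None refers to the upload.

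**What the scores cover.** For the PSS: "Participants rate each item based on their recall of the past month". The DSMQ-R "asks the patient about their self-management based on the previous days". The protocol gives no recall period for the WHO-5, PAID or SDSCA.

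**The analysis that joins them.** Section 10: "The association between glucose variability and parameters for distress, well-being and self-management will be analysed using multivariate regression analysis".

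**The concern.** The regression uses two measurements per patient, and each has its own clock. The glucose SD looks back from the upload; the PSS and DSMQ-R look back from questionnaire completion. No rule ties the two dates together or caps the distance between them. The only bound is that the upload falls during quarantine. A patient whose upload and questionnaire are weeks apart contributes a glucose week that the scores do not describe.

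What is at stake is a stated secondary objective. Section 2 asks for the association between self-management and glycaemic control. The HbA1c model in section 10.2 includes WHO-5, PSS and PAID but no self-management score. The five further models in that section have DSMQ-R scores as outcomes and list no glycaemic predictor. The glucose-variability regression in section 10 is therefore the only planned regression relating self-management to a glycaemic measure, and the DSMQ-R has the shorter of the two stated recall periods. A real association there could be weakened or distorted.

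**Working it through.** **1. The plan's own sample size.** Section 4.4 uses a difference of 4.0 mmol/mol, SD 11, alpha 0.05 and power 90%. Two-sided, two-group formula: n = 2 × (11 × (1.960 + 1.282) / 4)² = 158.9, so 159 per diabetes type, as stated. Invitations: 159 / 0.35 / 0.80 = 567.9, so 568 per type and 1136 in total, as stated. These figures concern HbA1c. The protocol gives no number of sensor wearers and no sample size for the glucose-variability regression, so they neither support nor weaken the point.

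**2. The dates side by side.**

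| Element | Looks back from | Length | Section |
|---|---|---|---|
| Glucose SD in quarantine | sensor upload | 1 week | 10.2 |
| PSS | questionnaire completion | past month | 10.2 |
| DSMQ-R | questionnaire completion | a few days, number not given | 10.2 |
| WHO-5, PAID, SDSCA | not stated | not stated | 10.2 |

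- Upload on the completion date: the glucose week lies inside the PSS month and covers the days just before completion. There is no misalignment, although one week is only part of the PSS month.
- Upload before completion: taking the month as 28 days, the glucose week stays inside it up to a gap of 28 − 7 = 21 days. The DSMQ-R overlap goes much sooner, once the gap exceeds the few days recalled.
- Upload 7 or more days after completion: the whole glucose week falls after the questionnaire and overlaps neither window.

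**3. Illustration of dilution.** All inputs here are assumed, because the protocol gives none: true correlation 0.30 between the score and the SD of the matched week; correlation (rho) of 0.6 to 0.8 between a patient's SDs in the matched and uploaded weeks; 85 wearers, the number giving 80% power when aligned. The model also assumes that the score relates to the uploaded week only through the matched week, and that the gap is unrelated to control or distress.

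Observed r = 0.30 × rho. The number needed at two-sided 0.05 and 80% power is n = (2.8016 / atanh(r))² + 3. Power = Φ(atanh(r) × √(n − 3) − 1.96).

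| rho | observed r | atanh(r) | n for 80% power | power, n = 85 | power, n = 159 |
|---|---|---|---|---|---|
| 1.0 (aligned) | 0.30 | 0.3095 | 85 | 80% | 97% |
| 0.8 | 0.24 | 0.2448 | 135 | 60% | 86% |
| 0.6 | 0.18 | 0.1820 | 240 | 38% | 62% |

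The calculation is for a single pair of variables, whereas the plan has several predictors. The last column shows how far the result depends on the unknown number of wearers.

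**The case against.** **The gap is inferred.** The reference to clinic practice may describe how the data are obtained rather than when. Fingerprick, sensor data and questionnaire are presented together after consent. Section 11.2 requires sensor data covering the quarantine period, which points to a late upload, and it also places the questionnaire late. If the three months in section 8.3 must reach back to the last pre-quarantine week, an upload could trail a questionnaire at two months by only about one month. This stands in part: nothing shows that gaps of weeks are typical. But a month is long against either stated recall period, and no rule prevents it.

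**The upload anchor is stated for the before/during comparison.** Section 10, where the regression appears, does not name the upload. True, but section 10.2 gives the only anchor for the quarantine SD anywhere in the protocol. This is a stated rule that an analyst would carry over, not a detail left open for the statistical analysis plan.

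**Recall windows are thin.** This stands. Only two of the five instruments have one, so a reader who infers that all distress, well-being and self-management scores are mismatched goes further than the document.

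**The dilution model is near the worst case.** This stands. If a score reflects a patient's usual variability, any week serves about equally well and the gap costs little. The assumed 0.6 to 0.8 also contains ordinary week-to-week noise that affects the matched week too.

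**The direction is not certain.** This stands. If poor control prompts a clinic contact and hence an upload, the bias can go either way.

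**Conclusion.** The point holds as a limited one. The stated rule ties the quarantine glucose week to the upload, no text ties the upload to the questionnaire, and section 10 analyses the two together. For the PSS and DSMQ-R the regression can therefore use a week that the scores do not describe.

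The effect tends towards dilution if upload timing is unrelated to control and distress; otherwise its direction is unknown. The protocol supplies neither the gap, nor the correlations, nor the number of wearers, so the size cannot be derived. An observed correlation of 0.18 to 0.24 in place of 0.30 is an upper-end case under assumed inputs. A reader might take the corresponding fall in power as the expected loss, or conclude that the association will be missed; the document supports neither.

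The reach is one secondary regression in sensor wearers. It matters because no other planned regression links self-management to a glycaemic measure. The primary HbA1c comparison, the before/during SD comparison and the HbA1c and DSMQ-R models in section 10.2 are unaffected. The change is worth making because it is cheap and gives a better rule than the present one.

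**What to change.** For the glucose-variability regression in section 10 only:

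- Compute the quarantine SD from the 7 days ending on the patient's questionnaire completion date, using quarantine days only, from the sensor data already retrieved under sections 8.3 and 11.2.
- Where the upload came before the questionnaire, use the nearest available week and record the gap in days.
- Repeat the regression in patients with short gaps, with the cut-off fixed before analysis.
- Optionally, repeat it for the PSS with a 4-week window ending on the completion date, as a sensitivity analysis. That window is too long for the DSMQ-R and should not be the main one.

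The before/during SD comparison keeps its present weeks.

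The cost is a few sentences of analysis wording and a date match. It needs no new data and adds no burden for patients. The downsides are a second SD window for one analysis, and incomplete overlap in patients who uploaded before the questionnaire. How many those will be cannot be told from the protocol, so the distribution of gaps should be reported.
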